7.2.6 Volume of Blood to Be Drawn from Each Subject

Table 4 Volume of Blood to Be Drawn from Each Subject

| | | Caucasian | | Japanese | |
|--|--|--------------------|-------------------|-------------------|-------------------|
| Assessment | | Sample Volume (mL) | Number of Samples | Total Volume (mL) | Number of Samples |
| Pharmacokinetic samples ^a | | 4 | 18 | 72 | 54 |
| Serum PTH sample ^a | | 2 | 2 | 4 | 2 |
| Pharmacodynamic samples ^a | | 6 | 5 | 30 | 15 |
| HBsAg, HIV, HCV ^a | | 8.5 | 1 | 8.5 | 1 |
| Safety | Biochemistry, FSH and β -hCG ^{a, b} | 8.5 | 5 | 42.5 | 9 |
| | Hematology ^a | 4 | 5 | 20 | 9 |
| Anti-PTH Antibody Samples ^a | | 3 | 2 | 6 | 2 |
| Total mL | | | | 183 | 437 |

β -hCG=beta-human chorionic gonadotropin; FSH=follicle stimulating hormone, HBsAg=hepatitis B surface antigen; HCV=hepatitis C virus; HIV=human immunodeficiency virus

^a If a catheter is in use for any blood draw or series of blood draws then the first 1mL is to be discarded. The 1mL discard has been taken into account in the table above and the total blood volume required for study.

^b β -hCG and FSH testing for females only.

During this study, it is expected that approximately 437mL of blood will be drawn from all subjects of Japanese descent, regardless of sex. For the non-Hispanic, Caucasian volunteers it is expected that 183mL of blood will be drawn, regardless of sex.

Note: The amount of blood to be drawn for each assessment is an estimate. The amount of blood to be drawn may vary according to the instructions provided by the manufacturer or laboratory for an individual assessment; however, the total volume drawn over the course of the study

should be approximately 183mL (non-Hispanic, Caucasian subjects) or 437mL (subjects of Japanese descent). When more than 1 blood assessment is to be done at the time point/period, if they require the same type of tube, the assessments may be combined.

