- On Day 1, all study subjects will receive rhPTH(1-84) as a single 100 μ g SC injection in the mid-thigh.
- On Day 4, and Day 7, all subjects of Japanese descent will receive rhPTH(1-84) as a single SC injection in the mid-thigh of either 25 μ g or 50 μ g depending upon randomization assignment. Administration of rhPTH(1-84) in subjects of Japanese descent in the mid-thigh should be randomized locally so that an equal number of subjects receive the first dose in the right thigh and an equal number in the left thigh. Subsequent doses should be administered in the opposing thigh to the last dose.

Assessments

[figure not shown]
- Serial blood samples for PK analysis will be collected on Day 1 (and Day 4 and Day 7 for the subjects of Japanese descent) for the determination of parathyroid hormone (PTH) concentrations at pre-dose and up to 24 hours post dose. These blood samples will be collected according to the Schedule of Assessments.
- Serial blood samples for PD analysis will be collected on Day 1 (and Day 4 and Day 7 for the subjects of Japanese descent) at pre-dose and up to 24 hours post dose for the determination of serum calcium, phosphate, and albumin concentrations.
- Safety and tolerability will be determined through assessment of treatment-emergent adverse events (TEAEs) from Day 1 time of dose up to the follow-up visit and vital signs, electrocardiogram (ECG) findings, and clinical laboratory evaluations on Day 1 pre-dose and up to 24 hours post dose for the non-Hispanic, Caucasian subjects and Day 1 pre-dose and up to 24 hours post last dose (Day 8) for the subjects of Japanese descent.
- Additional blood samples for safety purposes will be collected for assessment of anti-PTH antibodies.

Follow-up

- A post treatment follow-up visit will be completed 30 (± 2) days after the last dose of investigational product for each subject.

Figure 1 Study Design Flow Chart

This study is an open-label study to evaluate the PK and PD profiles, safety, and tolerability of single doses of rhPTH(1-84) in healthy adult subjects of Japanese descent (Group B) and matched healthy, adult non-Hispanic, Caucasian subjects (Group A). Group A and Group B need not be dosed at the same time.

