2.2 Randomization

Subject numbers are assigned to all subjects as they consent to take part in the study. Within each site (numbered uniquely within a protocol), the subject number is assigned to subjects according to the sequence of presentation for study participation. This will be a 4-digit number starting at 0001.

For eligible subjects, the subject number will be the identifying number used throughout the CRF.

The actual dose (either 25 μ g or 50 μ g) given to Group B (subjects of Japanese descent) on Day 4 and Day 7 is determined by a randomization schedule. The randomization schedule was produced by Shire Biostatistics. Japanese subjects will be randomized to receive either 25 μ g on Day 4 and 50 μ g on Day 7, or 50 μ g on Day 4 and 25 μ g on Day 7 in a 1:1 ratio.

Administration of rhPTH(1-84) in subjects of Japanese descent in the mid-thigh should be randomized locally so that an equal number of subjects receive the first dose in the right thigh and an equal number in the left thigh. Subsequent doses should be administered in the opposing thigh to the last dose.

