^k There must be a minimum washout period of 72 hours (maximum 73 hours) from dose to dose for the volunteers of Japanese descent.

^l SAEs will be followed to resolution

Table 2 Detailed Schedule of Assessments (non-Hispanic, Caucasian Subjects)

Study Day	Day 1																	Day 2	
	Pre Dose 1	Pre Dose 2	0	10m	20m	30m	45m	1h	1.25h	1.5h	2h	2.5h	3h	4h	6h	8h	12h	16h	
Physical examination ^a																			X
Vital signs (BP, temperature and pulse) ^{a,b}		X ^e						X					X	X					X
TriPLICATE Electrocardiogram (12-lead) ^{a,c}		X ^e																	X
Biochemistry, hematology, and urinalysis ^a		X ^e																	X
Serum β-hCG Pregnancy test (females only) ^a																			X
Investigational drug administration			X																
Pharmacodynamic blood sampling ^d		X ^e												X	X	X			X
Anti-PTH antibody sampling		X ^e																	
Pharmacokinetic blood sampling	X ^f	X ^e		X	X	X	X	X	X	X	X	X	X	X	X	X	X	X	

BP=blood pressure; ECG=electrocardiogram; PK=pharmacokinetic, PTH=parathyroid hormone

^a In the event a subject is prematurely discontinued from the study or withdraws, every attempt should be made to complete these assessments.^b Vital signs will be obtained while subject is supine at times noted. Temperature only to be obtained at screening and at predose on Day 1.^c Electrocardiograms will be performed in triplicate at each timepoint.^d Pharmacodynamic blood sampling assessments will include serum calcium and phosphate and must be drawn before PK samples at the same timepoint.^e These assessments should be performed within 30 minutes prior to dose administration. The urine collection may be the first void of the day [providing that it is predose] but may be outside the 30 minute window if necessary.^f These assessments should be performed within 90 (±30) minutes prior to dose administration.

Table 3 Detailed Schedule of Assessments (Subjects of Japanese Descent)

Study Day	Days 1, 4 and 7																		Days 2, 5 and 8
	Pre-dose 1	Pre-dose 2	0	10m	20m	30m	45m	1h	1.25h	1.5h	2h	2.5h	3h	4h	6h	8h	12h	16h	
Hour (relative to dosing time)																			24h
Physical examination ^a																			X ^h
Vital signs (BP, temperature and pulse) ^{a,b}		X ^e						X					X		X				X
TriPLICATE Electrocardiogram (12-lead) ^{a,c}		X ^e																	X
Biochemistry, hematology, and urinalysis ^a		X ^e																	X
Serum β-hCG Pregnancy test (females only) ^a																			X ^h
Investigational drug administration			X																

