11. SAFETY ANALYSES

The safety analysis will be performed using the Safety Analysis Set. Safety variables include AEs and TEAEs, clinical laboratory variables, vital signs, and ECG variables. For clinical laboratory and vital sign variables, the last value collected before the dose administration will be used as baseline for all analyses of that safety variable in the respective dose interval. Thus there will be a different baseline for each dose for the Japanese subjects.

Follow-up visits will be summarized under the 100 μ g dose, regardless of which sequence the subject was randomized to, or which doses they had received.

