11.1 Adverse Events

Adverse events will be coded using Version 20.0 or newer of MedDRA.

An AE (classified by preferred term) that occurs during the study will be considered a TEAE if it has a start date/time on or after the first dose of investigational product or if it has a start date before the date of the first dose of investigational product, but increases in severity or intensity on or after the date/time of the first dose of investigational product. If more than 1 AE with the same preferred term is reported before the date of the first dose of investigational product, then the AE with the greatest severity will be used as the benchmark for comparison to the AEs occurring during the study under the preferred term. An AE that occurs after follow-up visit will not be counted as a TEAE. However, any SAE that occurs after the follow-up visit and is considered related should be counted as a TEAE.

Adverse events will be allocated to a dose by assigning them to the last dose taken at the time of the onset of the AE.

An overall summary of the number of subjects with TEAEs will be presented by ethnic group and dose at onset, including the number and percentage of subjects with any TEAEs, serious TEAEs, TEAEs related to investigational product, TEAEs leading to discontinuation of investigational product, severe TEAEs, and deaths.

The number and percentage of subjects reporting TEAEs for each ethnic group and dose at onset will be tabulated by system organ class (SOC) and preferred term; and by SOC, preferred term, and maximum severity. TEAEs considered related to investigational product will also be summarized by SOC and preferred term. If more than 1 AE occurs with the same preferred term for the same subject, then the subject will be counted only once for that preferred term using the most severe occurrence for the summarization by severity. Serious TEAEs and TEAEs leading to discontinuation of investigational product will be summarized by SOC, preferred term, ethnic group and dose at onset.

Listings will be produced for all AEs (including pre-treatment AEs), SAEs, AEs considered related to investigational product, AEs leading to discontinuation of investigational product, and deaths.

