11.2 Clinical Laboratory Variables

Descriptive statistics for clinical laboratory values (in SI units) and changes from baseline at each assessment time point as well as shift tables from baseline to each visit for quantitative variables will be presented by ethnic group and dose for the following clinical laboratory variables.

Hematology Hemoglobin, hematocrit, red blood cells (RBC), platelet count, white blood cell count – total and differential (WBC), total neutrophils (absolute), eosinophils (absolute), monocytes (absolute), basophils (absolute), lymphocytes (absolute).

Biochemistry Sodium, phosphorus, β -hCG^b, potassium, total protein, magnesium, glucose, total CO₂ (Bicarbonate), PTH^c, blood urea nitrogen, albumin, FSH^b, creatinine, aspartate transaminase (AST), calcium, alanine transaminase (ALT), chloride, gamma glutamyl transferase (GGT), thyroid stimulating hormone (TSH)^a, alkaline phosphatase (ALP), thyroxine (T₄ total)^a, total bilirubin, triiodothyronine (T₃)^a, uric acid.

CO₂=carbon dioxide; FSH=follicle stimulating hormone; T₃=triiodothyronine; T₄=thyroxine; TSH=thyroid stimulating hormone

^a See Table 1, Table 2, and Table 3.

^b Females only.

^c Parathyroid hormone at screening and Day -1 is for baseline eligibility use only and not for PK analysis.

Urinalysis pH, glucose, protein, blood, ketones, bilirubin, nitrites, leukocyte esterase, specific gravity.

Clinical laboratory test values are potentially clinically important (PCI) if they meet either the low or high PCI criteria listed in Table 4. The number and percentage of subjects with post-baseline PCI values will be tabulated by ethnic group and dose. The percentages will be calculated relative to the number of subjects with available assessments at that dose level. The numerator is the total number of subjects with at least 1 post-baseline PCI value at that dose level. A supportive listing of subjects with post-baseline PCI values will be provided including the subject number, ethnic group, dose, baseline, and post-baseline values.

Listings for serum and urinary clinical laboratory results will be produced for all patients in the Safety Analysis Set. Clinically potential important test results will be listed as well.

Table 4 Criteria for Potentially Clinically Important Laboratory Tests

Parameter	Classification (on CDRs)	Criteria
Biochemistry		
Sodium	HIGH	> 5 mmol/L (5 mEq/L) above ULN
	LOW	> 5 mmol/L (5 mEq/L) below LLN

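### Follow-up results are all reported under 100 µg, which gives the Japanese 100 µg laboratory PCI count two scheduled assessments against one at 25 and 50 µg and mislabels the follow-up row elsewhere

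*SAP*

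**What the plan says.** **The attribution rule.** SAP section 11 places follow-up visits under 100 µg "regardless of which sequence the subject was randomized to, or which doses they had received". No reason is given.

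**Dosing and timing.** SAP 2.1 states "On Day 1, all study subjects will receive rhPTH(1-84) as a single 100" µg injection. SAP 2.2 states that the 25 or 50 µg dose "given to Group B (subjects of Japanese descent) on Day 4 and Day 7 is determined by a randomization schedule". Footnote k to SAP Table 1 adds "There must be a minimum washout period of 72 hours (maximum 73 hours) from dose to dose" for Japanese subjects. Follow-up is 30 (±2) "days after the last dose of investigational product for each subject" (SAP 2.1). SAP Table 1 schedules laboratory tests, vital signs and triplicate ECG at that visit.

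**Other attribution rules in the SAP.** Adverse events are allocated by "assigning them to the last dose taken at the time of the onset of the AE" (11.1). Discontinuations go to the last dose received (section 5). For concomitant medication, the follow-up period belongs to the last dose (section 9).

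**How abnormal values are counted.** For laboratory tests, SAP 11.2 says: "The numerator is the total number of subjects with at least 1 post-baseline PCI value at that dose level". Vital-sign PCI values are counted by dose and time point (11.3), and ECG PCI values by dose and visit (11.4). Laboratory and ECG shifts are tabulated from baseline to each visit.

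**The ethnic comparison.** Protocol 9.9.2 bases the direct safety comparison between the groups on the 100 µg data.

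**The concern.** For a Japanese completer, the follow-up visit belongs to the interval after the Day 7 dose, which is 25 or 50 µg. Reporting it under 100 µg has three consequences.

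- A laboratory abnormality first found at follow-up can count under 100 µg while the adverse event it triggers counts under 25 or 50 µg.
- The 100 µg column of the laboratory PCI table has an extra scheduled chance to record an abnormal value. That table serves the secondary objective on safety at 25, 50 and 100 µg in Japanese subjects, and a reader could take the excess for a dose-response.
- In the comparison between ethnic groups, a row labelled 100 µg reflects three doses in one group and one dose in the other.

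**Working it through.** **1. Check the visit count against the plan's own figure.** From SAP Tables 1 to 3, scheduled biochemistry and haematology samples are:

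- Caucasian: screening, Day -1, Day 1 pre-dose, Day 2, follow-up = 5.
- Japanese: screening, Day -1, Days 1, 2, 4, 5, 7 and 8, follow-up = 9.

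Protocol Table 4 gives 5 and 9, and 5 × 8.5 mL = 42.5 mL, as it states for Caucasian biochemistry. The visit list is therefore right.

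**2. Time from the 100 µg dose to follow-up.** Japanese subjects have two intervals of 72 to 73 hours, about 6 days, before the last dose. Then 6 + 28 = 34 and 6 + 32 = 38 days. Caucasian subjects: 28 to 32 days. Total dose before follow-up: 100 + 50 + 25 = 175 µg against 100 µg.

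**3. Scheduled post-baseline laboratory assessments per column.** Under SAP section 11, each pre-dose sample is the baseline for the dose that follows. I count it as baseline only.

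- Japanese 100 µg: Day 2 and follow-up = 2.
- Japanese 25 µg and 50 µg: one 24-hour sample each = 1.
- Caucasian 100 µg: Day 2 and follow-up = 2.

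**4. Effect on the PCI count with no drug effect.** The documents give no PCI probability, so p per parameter per visit is an assumption. With k independent assessments, P(at least one PCI value) = 1 − (1 − p)^k. Expected subjects = 12 × P.

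| Assumed p | 25 or 50 µg (k = 1) | 100 µg (k = 2) | Ratio | Expected of 12 |
|---|---|---|---|---|
| 1% | 1% | 1.99% | 1.99 | 0.12 v 0.24 |
| 5% | 5% | 9.75% | 1.95 | 0.60 v 1.17 |
| 10% | 10% | 19% | 1.90 | 1.20 v 2.28 |
| 20% | 20% | 36% | 1.80 | 2.40 v 4.32 |

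If a subject is abnormal at both visits or at neither, P = p for either k and the ratio is 1.

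**5. The other tables.** Vital-sign PCI, ECG PCI and the shift tables are laid out by time point or visit. Follow-up is a separate row there and does not inflate the 24-hour row. Only its dose label is wrong.

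**6. Would last-dose attribution be better?** About 6 of 12 Japanese subjects would have follow-up under 25 µg and 6 under 50 µg. At p = 5% the expected counts are 12 × 0.05 = 0.60 for Japanese 100 µg, 6 × 0.05 + 6 × 0.0975 = 0.885 at each lower dose, and 12 × 0.0975 = 1.17 for Caucasian 100 µg. The comparison between ethnic groups would then have 1 assessment against 2. A separate follow-up row gives 1 in every column.

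**The case against.** The case for leaving the rule alone has substance. The analyses are declared exploratory (SAP 2.6), there are 12 subjects per group, and no safety test is planned. The rule is prespecified, and subjects with PCI values are listed with their dose, baseline and values. Protocol 3.2 says PTH returns to baseline at about 12 hours, so a value 30 days later says little about any dose. Reporting follow-up under 100 µg also points to the Day 1 pre-dose baseline, the only untreated one in Japanese subjects, although the SAP does not give this as its reason.

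Many PCI criteria need both an out-of-range value and a sizeable change, which keeps background rates low. Others need no change from baseline (fasting glucose at or below 4.2 mmol/L, neutrophils below 40% or above 70%), so background hits in healthy volunteers are plausible.

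These points limit the consequence. They do not justify the label or the unequal count.

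Three stronger readings are tempting, and the documents do not support them.

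- *That vital-sign, ECG and shift results are inflated too.* They are tabulated by time point or visit, so they are not.
- *That the ethnic comparison has unequal numbers of assessments.* Both groups have two under 100 µg. What differs is exposure before follow-up.
- *That greater blood sampling produces a false 100 µg signal in haemoglobin or haematocrit.* Protocol 7.2.6 does say "it is expected that approximately 437mL of blood will be drawn from all subjects of Japanese descent", against 183 mL in Caucasian subjects. But nothing in the documents estimates what remains of that difference 28 to 32 days after the last dose. The PCI rules are also strict: haemoglobin below 100 g/L with a fall of at least 20 g/L, and haematocrit at or below 0.6 × LLN with a fall of at least 0.06 L/L.

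**Conclusion.** The concern holds with limited scope. The 100 µg attribution is inaccurate for every Japanese completer and departs from the SAP's own last-dose rules. In the laboratory PCI table alone, it gives Japanese 100 µg two scheduled assessments against one each at 25 and 50 µg. That 2-to-1 count follows from the schedule, provided each pre-dose sample counts only as the next dose's baseline.

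The resulting rate ratio rests on assumptions. It is 1.8 to 2.0 for p from 1% to 20% with independent visits, which is an upper bound, and it approaches 1 when abnormality persists within subjects. In the other safety tables the fault is the row label. In the ethnic comparison, the follow-up row mixes three doses (175 µg) with one (100 µg) and should not be presented as 100 µg data. The pharmacokinetic objectives are unaffected.

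**What to change.** Replace the sentence in SAP section 11 with: *Follow-up results will be summarised by ethnic group in a separate Follow-up (after last dose) row, with change from the Day 1 pre-dose value, and will not be attributed to any dose.*

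In SAP 11.2, state that by-dose laboratory PCI counts use all post-baseline values, including unscheduled ones, from that dose until the next dose or, for the last dose, until before the follow-up visit. Say explicitly that the pre-dose sample serving as the next dose's baseline is not also counted under the previous dose. Otherwise the first two dosing periods would each gain an assessment that the third lacks. Show follow-up PCI counts separately by ethnic group.

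The window should not be cut at 24 hours. SAP 18.3 uses all post-baseline assessments for PCI determination, and a 24-hour limit would drop later unscheduled values from the by-dose counts.

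The cost is SAP wording and one extra row or table block. No new data are needed and no result is lost. The difference in exposure between the ethnic groups at follow-up remains, but it is no longer labelled as a 100 µg result.

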11.1 Adverse Events

Adverse events will be coded using Version 20.0 or newer of MedDRA.

An AE (classified by preferred term) that occurs during the study will be considered a TEAE if it has a start date/time on or after the first dose of investigational product or if it has a start date before the date of the first dose of investigational product, but increases in severity or intensity on or after the date/time of the first dose of investigational product. If more than 1 AE with the same preferred term is reported before the date of the first dose of investigational product, then the AE with the greatest severity will be used as the benchmark for comparison to the AEs occurring during the study under the preferred term. An AE that occurs after follow-up visit will not be counted as a TEAE. However, any SAE that occurs after the follow-up visit and is considered related should be counted as a TEAE.

Adverse events will be allocated to a dose by assigning them to the last dose taken at the time of the onset of the AE.

An overall summary of the number of subjects with TEAEs will be presented by ethnic group and dose at onset, including the number and percentage of subjects with any TEAEs, serious TEAEs, TEAEs related to investigational product, TEAEs leading to discontinuation of investigational product, severe TEAEs, and deaths.

The number and percentage of subjects reporting TEAEs for each ethnic group and dose at onset will be tabulated by system organ class (SOC) and preferred term; and by SOC, preferred term, and maximum severity. TEAEs considered related to investigational product will also be summarized by SOC and preferred term. If more than 1 AE occurs with the same preferred term for the same subject, then the subject will be counted only once for that preferred term using the most severe occurrence for the summarization by severity. Serious TEAEs and TEAEs leading to discontinuation of investigational product will be summarized by SOC, preferred term, ethnic group and dose at onset.

Listings will be produced for all AEs (including pre-treatment AEs), SAEs, AEs considered related to investigational product, AEs leading to discontinuation of investigational product, and deaths.

